patients will be enrolled. As this is a competitive enrollment study, MUSC will enroll up to 75 volunteers. Eligibility will be determined by each site PI. The PI or Co-I will explain the study to qualified subjects prior to obtaining consent. The subject will also be given an opportunity to review and sign documentation of HIPAA compliance and authorization.

Inclusion criteria:

Patients to be included for participation in this study are:

- 1) Patients with a solid lung lesion 1.5-5cm identified on chest CT (obtained within previous 3 months) with the intention to undergo bronchoscopic evaluation. If the lesion is partially solid (i.e. there is a ground glass component) then the solid portion must make up >75% of the lesion and measure at 1.5-5cm. The decision to pursue biopsy will be made by the treating physician and agreed upon by the patient. This will include patients determined to have an intermediate risk of malignancy (5-65%) and those non-surgical candidate with higher risk lesions in need of diagnosis for alternative treatment. OR
- 2) Patients with a solid lung lesion 1.5-5cm identified on chest CT (obtained within previous 3 months) that are surgical candidates with a high probability of cancer (>65%) will be referred for surgical evaluation. If the lesion is partially solid (i.e. there is a ground glass component) then the solid portion must make up >75% of the lesion and measure at 1.5-5cm. If the patient refuses surgery or if the surgeon requests a definitive diagnosis prior to surgery the patient will have the option to be included in this study. All sites will use the same online calculator to document probability of malignancy.
- 3) Patients whose targeted lung lesion is visualized with fluoroscopy
- 4) Are at least 22 years old,
- 5) Lack Bleeding disorders, and
- 6) Are able to provide informed consent.

Race and gender inclusion will reflect the population characteristics found in the respective regions.

Exclusion criteria:

Patients to be excluded from participation in this study are:

- 1) Patients with a pure ground-glass opacity identified on chest CT
- 2) Patients with endobronchial involvement seen on chest CT.
- 3) Patients who refuse to participate,
- 4) Are less than 22 years of age,
- 5) Lack fitness to undergo flexible bronchoscopy as determined by the bronchoscopist prior to procedure, and
- 6) Are unable to provide informed consent
- 7) Pregnant

INFORMED CONSENT:

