Informed consent will take place in a private environment (e.g. patient exam room), free from distractions. The PI or sub-PI will approach the subject at their standard of care clinic appointment or prior to their scheduled bronchoscopy and will explain the study to qualified subjects prior to obtaining consent. All individuals who obtain consent (PI, Co-I, and study coordinators) have completion certificates for the CITI Human Subjects Research Education Course. Interviews to obtain consent will not follow any stressful situation (e.g. patient being informed he/she may have cancer) and will not be conducted if patient has received any mind-altering medications or anesthesia. Patients will be assessed for their capacity to consent by the ability to show comprehension of the procedure, ask appropriate questions, and appear properly oriented. A signed copy of all consents and the HIPAA authorization document will also be given to consenting subjects.

SUBJECT RANDOMIZATION

Once informed consent is obtained, the site PI will open the next randomization envelope to reveal the assigned procedure. Randomization envelopes are provided by MUSC and are to be opened in order, as indicated by the numbering on the exterior of the envelope. Inside each envelope is the randomization assignment for that subject. The randomization schedule is determined in advance by a computer with the plan for 1:1 randomization overall.

BRONCHOSCOPY PROCEDURES:

Patients will be randomized in a 1:1 fashion (107 in each arm) to undergo (1) standard FOB with fluoroscopy, or (2) R-EBUS with ultrathin bronchoscope (4.2 mm outer diameter with a 2 mm working channel) and guide sheath. This sample size will provide 85% power to detect a 20% improvement in yield using R-EBUS with fluoroscopy. This assumes a diagnostic yield for standard FB with fluoroscopy of 50% and R-EBUS with fluoroscopy is 70%. This also assumes 2-sided hypothesis testing and an alpha level (i.e. significance level) of 0.05. If subjects have multiple pulmonary lesions, it will be predetermined which lesion will be targeted. After informed consent and randomization have been performed, the following will occur:

(1) *Prior to bronchoscopy:* CT images will be obtained within 3 months of bronchoscopy and readily available for viewing during the bronchoscopic procedure. A de-identified copy of the CT and/or PET/CT report will be sent to the coordinating site (MUSC).

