- (2) *At bronchoscopy:* Moderate or deep sedation will be administered as deemed clinically appropriate by the procedure team. The time the bronchoscope is inserted and removed will be recorded. When sufficient sedation has been given, the bronchoscope (standard adult FB (Olympus BF-180 or 190) or ultrathin depending on randomization) will be introduced into the airway. Topical anesthesia with 1%- 2% lidocaine will be administered to the vocal cords,

trachea, and right and left mainstem bronchi through the bronchoscope. The bronchoscope will be advanced as distally as possible under direct visualization. In cases in which the lesion cannot be located, the clinical judgment of the site PI will direct one or more of the following choices:

- abort the procedure
- crossover to standard bronchoscopy and brushing
- BAL under fluoroscopy (even when lesion is not visualized under ultrasound)
- another standard of care procedure

(3) For Bronchoscopy plus R-EBUS:

Once the ultrathin bronchoscope has been passed as distally as possible, the R-EBUS will be utilized. Depending on the number of generations of bronchi that are passed, a guide sheath (Olympus; external diameter 2mm [K201]) may be inserted into the ultrathin scope. The 20MHz mechanical R-EBUS probe (Olympus, UM-S20-17S) +/- the guide sheath covering will be introduced into the working channel of the bronchoscope and advanced to the lesion. An attempt to definitively locate the lesion with R-EBUS will be made. Fluoroscopy will be used to aide in locating the lesion, which will then be verified by R-EBUS. A de-identified jpeg image of the ultrasound image will be recorded and subsequently uploaded to the REDCap study data collection instrument. Once the lesion is located, the R-EBUS probe will be removed. The guide sheath will remain in place. Bronchial brush (Olympus BC-204D-2010 followed by a smooth transbronchial biopsy forceps (Olympus FB-233D) will be introduced through the working channel with guide sheath to obtain pathologic and cytologic specimens. 1 brushing (standardized to 10 strokes per brushing) will be performed followed by 5 transbronchial forceps biopsies. (Brush preparation: smear brushing sample, then cut brush and drop into cytolyte; fix slide with alcohol.) The R-EBUS probe will be reinserted after obtaining specimens to again verify the location of the lesion.

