If a diagnosis is not obtained after the procedure, further recommendations regarding treatment will be made by the treating physician. (i.e. follow-up CT chest, CT guided transthoracic needle aspiration, or surgery). In the standard FB arm, the bronchoscopist will have the option of using peripheral ultrasound with or without the ultrathin scope to attempt to identify the lesion. Specimens obtained must be kept separate and identified as having performed using R-EBUS (e.g. labelled "radial brush", "radial biopsy") and reflected in the case report form. If ROSE is non-diagnostic and/or indicates chronic inflammation, crossover to the Ultrathin bronchoscope with R-EBUS will take place. In those patients that cross over to the Ultrathin bronchoscope with R-EBUS the same protocol for those randomized to the ultrathin/R-EBUS arm will be followed (see #3).

RISKS OF PROCEDURES:

The greatest risks from bronchoscopy are related to moderate or deep sedation and the very act of passing a bronchoscope into the airway. To mitigate risks of bronchoscopy all patients will be monitored by a nurse and a respiratory therapist during the procedure. In addition, oxygen saturation (using pulse oximetry) respiratory rate, blood pressure, ECG, and heart rate will be continuously monitored. Patients will not be released until they are fully awake and medically stable.

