Each site investigator will review the results, and the results will become part of the subject's medical record and research record. Any clinical follow-up or repeat procedures will be dictated by the patient's physician based on clinically relevant data and will not be influenced by enrollment into this study. To protect subject

confidentiality, MUSC will receive all sites' data as de-identified through use of the 6 digit patient codes. All information and data related to this study will be stored in a secured, locked cabinet in MUSC Clinical Sciences Building Room 809. The privacy of subjects will be protected using a 6 digit computer generated random code. The key to the code will be kept in a password protected folder on the MUSC DB2 (\DA) server; access to this folder is restricted to study personnel alone.

Electronic Data will be entered and stored in the secure REDCap database created for this study. REDCap is a web-based application designed exclusively to support data capture for research studies. It provides an intuitive interface for data entry, audit trails for tracking data manipulation and export procedures, procedures for importing data from external sources, advanced features such as branching logic and calculated fields, and automated export procedures for seamless data downloads to common statistical packages such as SPSS, SAS, Stata, and R. It was developed at Vanderbilt University (see <http://redcap.vanderbilt.edu/consortium/index.php>) and is ideal for remote data entry, as will be the case for this multi-center trial.

III. STATISTICAL ANALYSIS:

Statistical comparisons will be made using chi-square analysis where applicable. Sensitivity, specificity, positive and negative predictive value and accuracy of all procedures will be calculated. A logistic regression analysis of factors influencing tissue quantity will be undertaken.

Coordinating Center: MUSC will be the designated coordinating center for this trial. MUSC will be responsible for development of the database, housing the data, working with the sites on IRB issues, patient enrollment, completion of on-line data collection instrument and validation of the data. MUSC will also be responsible for payment to the sites when a patient's case report form is complete and query-free. Statistical support and interim analysis will be performed at MUSC by an in house statistician ([name]). Interim results will be shared with all participating sites during teleconference meetings.

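### Interim results are to go to all participating sites, with nothing limiting them to pooled data, although operators know the allocation and keep some, limited, discretion

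*Combined protocol and SAP*

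**What the plan says.** **Sharing.** The Coordinating Center paragraph (section III, STATISTICAL ANALYSIS) has two relevant sentences: "Statistical support and interim analysis will be performed at MUSC by an in house statistician" and "Interim results will be shared with all participating sites during teleconference meetings". The number, timing and purpose of interim analyses are not given, and no passage restricts what sites see to pooled data.

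**Who holds the data.** The same paragraph says "MUSC will be responsible for development of the database, housing the data". Under SUBJECT ENROLLMENT that centre may also enrol up to 75 of the 214 patients. Nothing in the text separates its own operators from results by arm.

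**Knowledge of allocation.** SUBJECT RANDOMIZATION: "the site PI will open the next randomization envelope to reveal the assigned procedure". The arms use different bronchoscopes, and no blinding of operators is described.

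**Discretion that remains.** BRONCHOSCOPY PROCEDURES item (2): "In cases in which the lesion cannot be located, the clinical judgment of the site PI will direct one or more" of several courses, including stopping, changing technique or doing another procedure. Item (3) makes the guide sheath optional.

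**Limits on discretion.**
- Items (3) and (4) fix sampling in both arms at one 10-stroke brushing and five forceps biopsies.
- Inclusion criterion 3 admits only "Patients whose targeted lung lesion is visualized with fluoroscopy".
- For R-EBUS used in the standard arm, item (6) requires: "Specimens obtained must be kept separate and identified as having performed using R-EBUS".

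**Crossover in the standard arm.** Item (6) says "the bronchoscopist will have the option of using peripheral ultrasound with or without the ultrathin scope to attempt to identify the lesion". The same item then says crossover is to happen if rapid on-site evaluation (ROSE) is non-diagnostic or shows chronic inflammation. DATA COLLECTION item (3) repeats this for chronic inflammation.

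**The concern.** Diagnostic yield depends partly on how hard the operator tries. The people who would receive interim results are the people who advance the bronchoscope, know the arm and decide what to do when the lesion cannot be found. If they learned part-way through which arm was ahead, they could give up or change technique sooner in the other arm. Yield there would then fall for reasons unrelated to the technique, and the final chi-square comparison would carry that difference as if it were a treatment effect.

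The coordinating centre is the sharpest case. It performs the interim analysis, houses the data and may enrol 75/214 = 35% of the patients.

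**Working it through.** **1. The plan's own figure.** Inputs from BRONCHOSCOPY PROCEDURES: yields 50% and 70%, two-sided alpha 0.05, 85% power, 107 per arm. With mean yield 0.60 and no continuity correction:

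n = [1.96 × √(2 × 0.60 × 0.40) + 1.036 × √(0.50 × 0.50 + 0.70 × 0.30)]² / 0.20² = [1.358 + 0.703]² / 0.04 ≈ 106.2, so 107 per arm.

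Approximate power at 107 is 85.3%, and exact binomial power of the uncorrected chi-square test is 85.0%. The plan's figure reproduces and is not in dispute.

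**2. What would have to happen for harm.**

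| Step | What the documents say |
|---|---|
| Results are shared during enrolment | Not dated. Non-diagnostic patients are followed for up to one year, so a look after the last enrolment is possible. |
| Results are shown by arm | Not stated, and not excluded |
| Operators know the arm | Yes |
| Operators can alter effort | Yes, but narrowly: lesion not located, guide sheath |
| Diagnoses are lost unequally between arms | Not known |

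**3. Illustration with losses in a pre-set arm.** The number of lost diagnoses, k, is an assumption. Let S and Y be independent binomial (107, p) counts and let X = S − k (not below zero). Reject when |X − Y|/107 exceeds 1.96 × √(2 × m × (1 − m)/107), with m = (X + Y)/214. Summing the exact probabilities over all pairs gives the false-positive rate:

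| True yield, both arms | k = 0 | k = 2 | k = 3 | k = 5 |
|---|---|---|---|---|
| 50% | 4.72% | 5.56% | 6.61% | 10.08% |
| 60% | 4.85% | 5.56% | 6.57% | 9.94% |
| 70% | 5.01% | 5.82% | 6.99% | 10.87% |

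If the same number is lost in both arms at 60%, the rate does not rise: 4.55%, 4.45% and 4.34% for k = 2, 3 and 5.

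**4. Illustration with losses in whichever arm is behind at halfway.** This is closer to the feared mechanism, because operators react to the interim result. With the same test at 60% yield, and k diagnoses removed from the second half of the trailing arm, the rate is about 8.6%, 11% and 18% for k = 2, 3 and 5.

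**5. Scale of the assumed losses.** With sharing at halfway, diagnoses still expected in one arm are 53.5 × 0.60 = 32.1. Losing 2, 3 or 5 of them is 2/32.1 = 6.2%, 3/32.1 = 9.3% or 5/32.1 = 15.6%. No passage indicates which of these, if any, is likely.

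**The case against.** The strongest case for leaving the plan alone has four parts.

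- **The content and timing of the sharing are inferred.** This is correct. A reader might take the sentence to mean that by-arm yield will be shown to sites while they recruit, but the documents do not say so. What stands is that an affirmative rule to share exists and nothing excludes that use.
- **Discretion is narrow.** This largely stands. Sampling is fixed in both arms, R-EBUS specimens in the standard arm are labelled separately, and fluoroscopic visibility of the target is an entry criterion. A reader might also infer that operators may freely choose R-EBUS after a failed standard procedure. The text does not support that, because item (6) also makes crossover mandatory on certain ROSE findings. What remains is the lesion that cannot be located and use of the guide sheath. Separate labelling does not protect effort before crossover or the decision to stop.
- **Operators already hold expectations.** The protocol tells them it assumes 50% against 70%, and site investigators review their own patients' results. This stands too: restricting interim results reduces the bias route but does not close it. A trial-wide comparison from the coordinating centre would still be more persuasive than one site's few patients.
- **The loss counts are invented.** They are assumptions, used only to show how sensitive the test is.

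**Conclusion.** The point holds in a limited form. The plan sets a rule to share interim results with every site, does not confine it to pooled data, and the recipients are unblinded operators with some discretion. Whether harm would follow depends on sharing during enrolment, by arm, with an unequal change in effort. None of these is stated, and the size cannot be derived from the documents.

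The illustrative rates (5.6% to 9.9% for a pre-set arm, about 8.6% to 18% for the trailing arm, at 60% yield and 2 to 5 assumed losses) are neither estimates nor bounds. In particular, the pre-set figures should not be read as a worst case, since the trailing-arm figures are higher.

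A reader might also infer an inflated type I error from interim testing. One unadjusted look at half the data, tested at 0.05, would give about 8.3% overall. The documents do not say that such a test or early stopping is planned, so this forms no part of the finding.

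The change is a cheap improvement, not a correction of a demonstrated error.

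**What to change.** Replace the sharing sentence in the Coordinating Center paragraph with:

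> Until enrolment and study procedures are complete, sites, including investigators at the coordinating centre, receive only enrolment, data-quality and pooled (both-arm) information; results by arm stay with the statistician, and with a medical monitor only if that person does not enrol or perform study procedures.

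This does not forbid an interim comparison. The purpose and timing of the interim analysis are for the sponsor to state.

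Separately, the optional and mandatory statements on R-EBUS after a non-diagnostic standard procedure (BRONCHOSCOPY PROCEDURES item (6), DATA COLLECTION item (3)) must be reconciled.

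**Cost.** Sites lose early sight of results by arm. The coordinating centre must restrict access to by-arm summaries, which takes some care: it houses the database, receives the pathology reports and enrols patients, and the lead investigator captures adverse events in REDCap. The medical monitor's role must be checked, because the DATA SAFETY MONITORING PLAN does not say whether that person is independent of the study procedures. No patients are added and no power is lost.
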